Study Name:

Urgent Care Management of Respiratory Illness Enabled with Novel Testing Pathway (URGENT): A Randomized Control Trial of Respiratory PCR versus Standard Care

Date: 30-January-2023

NCR: NCR213901

Principal Investigator:

Name: **[name] MD, MS**
Title: **Associate Professor of Emergency Medicine**
Institution: **George Washington University**

Background

Over the past two decades, new options have emerged for patients seeking acute care such as urgent care, retail clinics, and telemedicine. While visits to emergency departments have declined overall since 2008, urgent care facilities have seen a more than 100-fold increase in patient traffic.⁶ For patients presenting to urgent care centers with acute respiratory illness, early and appropriate treatment is essential in lessening the disease course and preventing its spread. Acute respiratory illnesses account for the largest percentage of urgent care center visits, however diagnosis of the specific pathology of the infection is challenging and reliant on traditional diagnostic tests and physical exams.⁷ In evaluating patients for acute respiratory illnesses, clinical findings are often nondescript and laboratory testing is needed for definitive diagnosis.¹ Many of the causative agents of acute respiratory illnesses are tested for using antigen detection assays.⁵ While these assays produce results in approximately 10-15 minutes, they have relatively poor sensitivity which can lead to missed diagnoses.³ Viral or bacterial cultures can also be used to diagnose acute respiratory illnesses, however, they take days to produce results which delays initiation of antiviral or antibiotic therapy and infection control measures.³

Rapid diagnosis and precise treatment have become possible with multiplex polymerase chain reaction (PCR) panels that can identify a variety of causative agents of acute respiratory illnesses such as bacterial and viral infections in one urgent care visit.⁴ While real-time PCR is currently used as a standard for diagnosing acute respiratory illnesses such as influenza due to its high sensitivity and specificity, it typically takes several hours for results which is unfavorable in the urgent care setting.² Highly sensitive and rapid random-access PCR tests provide the sensitivity and specificity needed to both rapidly and accurately diagnose acute respiratory illnesses.² Similar PCR panels have been used in previous research for the diagnosis of gastrointestinal illnesses in the emergency department and point-of-care testing for hospitalized adults presenting with acute respiratory illness.¹ In this study, we aimed to determine if a rapid multiplex PCR test for urgent care patients with symptomatic upper respiratory infections can improve patient and provider-reported outcomes. Acute respiratory illnesses cause millions of cases per year in the US and result in countless hospitalizations, which the current COVID-19 pandemic has greatly inflated. Most upper respiratory infections are of viral etiology.⁷ Rapid diagnostics for acute respiratory illnesses in urgent care centers would be highly beneficial in improving both patient outcomes and care experiences as well as guiding provider course of care. In a 2010 study, 33.3% of urgent care center visits were found to be due to upper respiratory infections.⁷ Furthermore, 41.5% of prescriptions written at urgent care facilities were found to be for antibiotics.⁷ Antibiotic overuse for acute respiratory illnesses is partly driven by clinical uncertainty regarding underlying etiology.¹ With the increasing threat of antimicrobial resistance (AMR), accurate and rapid diagnostics will aid in preventing unnecessary antibiotic prescribing and promote antimicrobial stewardship.

Introduction of the rapid testing panels for acute respiratory infections in urgent care settings will afford clinicians ease in diagnosing the cause of a patient's illness which will in turn lead to better patient outcomes. This study utilizes the Biofire®

FilmArray Panel which in previous studies has been shown to be highly effective in diagnosing acute respiratory illnesses.

Study Objectives:

Aim 1: To asses improvement in *patient*-reported outcomes (PRO) in Urgent Care patients with acute respiratory illness who are tested with RP2.1 (EXP) versus standard care (SC).

Hypotheses: Improvement in PRO's in group (tested with RP2.1 (EXP) vs. standard care (SC)) assessed at Day 0 (i.e., day of test) and/or Day 7 (call-back).

Outcomes

Primary:

- ***Satisfaction with Urgent Care*** (willingness to recommend urgent care versus others). Day 0.

Secondary:

- ***Satisfaction with Urgent Care*** (willingness to recommend urgent care versus others). Day 7.
- ***Time isolated*** (or recommended to isolate) by patient. Day 0,7.
- ***Time isolated*** (or recommended to isolate) by family members / close contacts. Day 0,7.
- ***Understanding of current disease process***. Day 0, 7
- ***Need for additional diagnostic tests by patient***. Day 7.
- ***Need for additional diagnostic tests of family members / close contacts***. Day 7.
- ***Missed time at work***. Day 7.

Aim 2: To determine the difference in Urgent Care *provider*-reported outcomes after treatment of patients with acute respiratory illness tested with RP2.1 vs. SC. Assessed by provider survey.

Hypothesis: Use of RP2.1 will lead to differences in provider-reported outcomes assessed at Day 0 compared to SC.

- ***Confidence in diagnosis***
- ***Recommendations regarding isolation***
- ***Ability to address patient needs/ questions***.
- ***Recommendations regarding disease course***.
- ***Follow up recommendations***

Study Synopsis

Study Design

Sites

Two GW Urgent Care sites (McPherson Square, Rhode Island Avenue) - also known as Immediate and Primary Care Sites (IPC)

Enrollment times

7.5 days per week, RA's screen for relevant chief complaint related to respiratory infection.

- (Estimate 5 hours per day = 25 hours / week) at all 3 sites. Therefore, 5 hours x 3 sites = 15 hours per day. Per week, 15 hours x 7 days / week = 105 hours / week
- Follow up and survey = 3 hours per day = 21 hours/ week
- $105 + 21 = \underline{136 \text{ RA hours per week}}$

Study Arms

EXP: RP2.1 result communicated plus scripted communication of meaning of results.
SC: Standard communication

Outcome Measures

Day 0

RA communicates results and assessment of Day 0 relevant patient, provider and process outcomes.

Day 7

Review of EHR (Allscripts, CRISP)

Patient follow-up assessment performed by phone.

Processing Samples

Samples will be collected and processed at the three urgent care/immediate primary care facilities (IPCs) affiliated with George Washington University Medical Faculty Associates.

- Testing will occur on site. Each urgent care performs CLIA-waived lab tests for point of care tests.
- Any Non- RP2.1 testing will be allowed in either group per discretion of the provider.
- Standardize script for communication of results provided on same day as testing to providers.

Standard care

Most patients with symptoms of a respiratory illness receive testing for COVID-19. The process for suspected COVID is to run a SARS antigen test initially. Results of the antigen tests are available within 15 to 20 minutes. For anyone with a negative test, samples are then sent to LabCorp for a confirmatory PCR test. The results of the PCR test are dependent on the number of tests LabCorp is performing but typically take

between 24 to 96 hours. All patients with results that are positive receive a phone call; for patients with a negative test, no call is made and patients must access the patient portal to get results.

Our expectation is that the use of RP2.1 will lead to improved satisfaction for patient and provider.

Inclusion Criteria

- Age 7-year-old
- Clinically stable
- Must present with one symptom of respiratory illness (e.g., cough, sneezing, runny or stuffy nose, sore throat, headaches, muscle aches, trouble breathing, shortness of breath, and/or fever).

Exclusion criteria

- Patient is unable to provide informed consent
- Chronic symptoms (>14 days) or asymptomatic
- Unstable (or “too sick” to consent)
- Prisoner or ward of state
- Non-English speaker

Potential barriers and solutions

- Success for the study requires provider buy-in to aid with recruitment efforts. Lack of provider buy-in may hinder sample size ascertainment. Proposed solutions include electronic alerts, incentive payments, and communication aids to physicians to discuss results with patients.
- Successful undertaking of this study requires dedicated research staff to ensure high recruitment goals and fidelity to protocol. We have budgeted for a study coordinator with 25% effort allocated directly to the project in addition to 136 hours of research assistant time per week. We currently have several trained research assistants who will be assigned to this study allowing for rapid implementation of study.

Data Analysis and Statistical plan

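### The arms differ in both the test and a scripted explanation of results, but the objective, the Aim 2 hypothesis and the stated expectation name only the test; the design supports a claim for the package

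*Protocol*

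**What the plan says.** The only definition of the arms is in the protocol's Study Synopsis, under Study Arms. The experimental arm is "EXP: RP2.1 result communicated plus scripted communication of meaning of results" and the control arm is "SC: Standard communication".

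Three statements of purpose name the test and leave out the script:

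- Background: "we aimed to determine if a rapid multiplex PCR test for urgent care patients" can improve patient and provider outcomes.
- Aim 2, Hypothesis: "Use of RP2.1 will lead to differences in provider-reported outcomes assessed at Day 0 compared to SC".
- Standard care: "Our expectation is that the use of RP2.1 will lead to improved satisfaction for patient and provider".

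Two places are looser. The title describes care "Enabled with Novel Testing Pathway", although its subtitle names only respiratory PCR. Aim 1 compares patients "tested with RP2.1 (EXP) versus standard care (SC", and the EXP label points back to the two-part arm definition.

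The script appears once more, under Processing Samples: "Standardize script for communication of results provided on same day as testing to providers". That line names no arm. Potential barriers and solutions also mentions communication aids for physicians, again without an arm. The SAP labels its two groups by the kind of assessment received and does not mention a script.

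**The concern.** When two things change together between randomised arms, the comparison estimates their joint effect. Here they are a rapid multiplex result and a scripted account of what it means. The sole primary outcome is willingness to recommend the urgent care site on Day 0, a subjective rating that a clearer explanation could raise whatever test lay behind it.

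Neither document drafts a conclusion. If the conclusion follows the Background objective or the Aim 2 hypothesis, a difference between arms will be reported as an effect of the PCR panel. A site that bought the panel without adopting the script would then be relying on a result the trial had not produced.

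**Working it through.** **1. What differs between the arms**

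| Component | EXP | SC |
|---|---|---|
| RP2.1 result | yes | no |
| Scripted communication of its meaning | yes (Study Arms) | not listed; standard communication |
| Non-RP2.1 testing | at provider discretion | at provider discretion |

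Two components differ. The only account of usual result communication, under Standard care, concerns COVID testing: positive patients are called, negative patients look in the portal. It mentions no script.

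**2. What each statement names**

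| Place in protocol | Test named | Script named | Package reading possible |
|---|---|---|---|
| Background objective | yes | no | not from its wording |
| Aim 1 | yes | no | yes, through the EXP label |
| Aim 2 hypothesis | yes | no | only if RP2.1 is read as shorthand for the arm |
| Standard care, expectation | yes | no | not from its wording |
| Title | yes | no | yes, through the pathway wording; the subtitle points to PCR |

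**3. Can the components be separated?** There is no arm with RP2.1 and no script, and none with standard testing and a script. The SAP plans only two-group comparisons (chi-squared or Fisher; t or Mann–Whitney). Nothing planned separates test from script.

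**4. Which outcomes are directly exposed?** Aim 1 lists 1 primary + 7 secondary = 8; Aim 2 lists 5; total 8 + 5 = 13. An explanation could directly move satisfaction at Day 0 (the primary), satisfaction at Day 7, understanding of the disease, and provider ability to address questions: 4 of 13. Counting each time point separately, understanding counts twice (4 + 1 = 5). The total becomes 16, because understanding and the two isolation outcomes each gain one (13 + 3). That gives 5 of 16. Which outcomes count as exposed is a judgement, and these are counts, not effect sizes.

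**5. Illustration under assumptions.** The protocol's planned enrolment reproduces as 30 per week × 12 weeks = 360. Assume 1:1 allocation (180 per arm), a two-sided 0.05 test, an SC rate of 60%, and no effect of the test itself. The 60% is borrowed from the SAP, where it concerns satisfaction with time to result. Let the script alone add d. With p₁ = 0.60, p₂ = 0.60 + d and p̄ their mean:

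power = Φ{[d − 1.96·√(2p̄(1−p̄)/n)] / √((p₁(1−p₁) + p₂(1−p₂))/n)}

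For d = 0.10, n = 180: √(2·0.65·0.35/180) = 0.0503 and √((0.24 + 0.21)/180) = 0.0500, so Φ{(0.10 − 0.0985)/0.0500} = Φ(0.029) = 0.51.

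| Assumed script effect (points) | Chance of a significant result, 180 per arm |
|---|---|
| 5 | 16% |
| 10 | 51% |
| 15 | 86% |
| 20 | 99% |

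The documents give no script effect, so the table is not evidence of size. It shows only that a significant result would not by itself identify the test as the cause. A smaller trial would give lower chances.

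**The case against.** The strongest reply is that this is a pragmatic trial of a testing pathway. Aim 1, which holds the only primary, labels its group EXP, and EXP is defined as result plus script. RP2.1 versus SC in Aim 2 may be shorthand for the same arms. Any test result comes with some explanation, and a script about an RP2.1 result could not be given unchanged to patients who have no such result.

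Much of this stands. The package comparison is legitimate, and no sentence expressly claims to isolate the test from its explanation. But if the trial is of a package, its purpose should be stated that way throughout. The Background objective and the Standard care expectation carry no arm label that would lead a reader back to the script.

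A second reply is that both arms may have had a script, since Processing Samples names no arm. That is possible, and the point would then shrink or disappear. It would also contradict the Study Arms entry, so the two places need reconciling either way.

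A third reply is that the SAP sizes the trial on satisfaction with time to result, which same-day testing could plausibly move more directly than a script. That is fair for that measure. The protocol's primary, however, is willingness to recommend.

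**Conclusion.** The point holds as a mismatch between the contrast and the wording of several aims. As the arms are written, a difference is an effect of RP2.1 plus scripted communication. It cannot be attributed to the test itself. This bears most on 4 of 13 listed outcomes, the only primary among them. How much of any difference the script would account for cannot be judged from the documents. The conclusion assumes that the script was used only in the experimental arm, as Study Arms implies.

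Three stronger readings are tempting and not supported:

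- A reader might infer that the protocol firmly claims an effect of the test in isolation. The EXP label in Aim 1 and the pathway wording in the title leave a package reading open, so the text is inconsistent.
- A reader might infer that the comparison is invalid. Randomised package against usual care is a valid contrast; only attribution is limited.
- A reader might extend the exposed outcomes to isolation, disease course and follow-up. The script's content is not given, so that would be an assumption.

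The Outcome Measures entry can be read as having the research assistant both communicate results and collect Day 0 outcomes. That is a separate measurement question and adds nothing to this point.

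**What to change.** 1. Reconcile Study Arms, which lists the script under EXP, with Processing Samples, which gives a script to providers without naming an arm. State who delivered it and in which arm.
2. Unless the same scripted communication was used in both arms, restate the objective, aims, hypotheses and conclusion as *RP2.1 plus scripted communication of results versus standard care*, and make no claim for the test without the script.
3. If the same script was used in both arms, say so and correct the SC line in Study Arms.

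The cost is wording and a narrower claim. Sample size, analyses and care in either arm are unchanged. The change can still be made if enrolment has closed, as the SAP's past tense suggests.

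### The research assistant role both communicates results and assesses the Day 0 outcomes, so the open, subjective primary is at risk of interviewer bias, most plausibly towards EXP; who delivers the script is also contradictory

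*Protocol*

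**What the plan says.** - **Day 0 tasks** (Protocol, Study Synopsis, Outcome Measures): "RA communicates results and assessment of Day 0 relevant patient, provider and process outcomes". One role is given both tasks.
- **Primary outcome** (Protocol, Study Objectives, Aim 1): satisfaction with urgent care, defined as "willingness to recommend urgent care versus others). Day 0". This is a patient opinion.
- **Arms** (Protocol, Study Arms): "EXP: RP2.1 result communicated plus scripted communication of meaning of results", against "SC: Standard communication".
- **Script** (Protocol, Processing Samples): "Standardize script for communication of results provided on same day as testing to providers". The section on potential barriers adds "communication aids to physicians to discuss results with patients".
- **Expected direction** (Protocol, Standard care): "Our expectation is that the use of RP2.1 will lead to improved satisfaction for patient and provider".
- **Staffing** (Protocol, Potential barriers and solutions): "We currently have several trained research assistants who will be assigned to this study".

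Neither the protocol nor the SAP mentions blinding, an assessor separate from the communicator, private or anonymous completion, or a standard way of asking for the rating.

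**The concern.** The arms are visibly different and the primary is an opinion about the visit. If the role that explains the result also collects the rating, patients may rate more kindly out of courtesy to someone who has just helped them. Communication is an added component of EXP, so this pressure could be stronger there. It could be weaker in SC: an antigen-negative patient waits a further 24 to 96 hours for PCR and receives no call if that is negative too, so some SC patients may have had less communication of results when they give the Day 0 rating.

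A courtesy effect that differs by arm cannot be separated from a treatment effect by the SAP's chi-squared, Fisher, t or Mann–Whitney comparisons, because it moves with the arm. Aim 2 could also be affected. If the RA delivers the script, the provider's rating of how well the patient's questions were addressed would partly reflect the RA's work, and only in EXP.

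**Working it through.** **Step 1: the text.** Set side by side, the protocol gives two accounts of who communicates.

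| Place | Who communicates |
|---|---|
| Outcome Measures, Day 0 | The RA, who also assesses outcomes; the recipient of the results is not named |
| Processing Samples | The script goes to providers |
| Potential barriers and solutions | Aids for physicians to discuss results with patients |

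On the first account, delivery of an EXP component and assessment of the primary sit in one role. On the other two, clinicians may do the delivering. On either account, nothing says how the patient's rating is collected.

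**Step 2: the documents' numbers.** Planned enrolment is 30 per week × 12 weeks = 360, or 180 per arm if allocation is 1:1 (the ratio is not stated). The SAP gives no N. Its inputs (90% v 60%, power 0.8, alpha 0.05, taken as two-sided) give

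n per arm = [1.960 × √(2 × 0.75 × 0.25) + 0.842 × √(0.9 × 0.1 + 0.6 × 0.4)]² / 0.30² = 31.5, so 32 per arm (64 in total).

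The 360 is thus an accrual figure. Both sizes are used below.

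**Step 3: what a reporting shift would do.** Assume no true effect, a dichotomised primary with favourable proportion p in SC, and p + d reported in EXP, where d is the net between-arm reporting shift. For a two-sided 0.05 two-proportion test without continuity correction:

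- SE₀ = √[2 × p̄(1 − p̄)/n], with p̄ = p + d/2
- SE₁ = √{[(p + d)(1 − p − d) + p(1 − p)]/n}
- P(reject) = Φ[(d − 1.96 SE₀)/SE₁] + Φ[(−d − 1.96 SE₀)/SE₁]

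Worked case, p = 0.60, d = 0.05, n = 180:

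- SE₀ = √(2 × 0.625 × 0.375/180) = 0.0510
- SE₁ = √[(0.2275 + 0.24)/180] = 0.0510
- P(reject) = Φ(−0.98) + Φ(−2.94) = 0.163 + 0.002 = 0.165

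The first term is rejection in favour of EXP, so nearly all false positives point that way.

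| SC rate | n per arm | d = 0 | d = 2 points | d = 5 | d = 10 | d = 15 |
|---|---|---|---|---|---|---|
| 60% | 180 | 5.0% | 6.7% | 16.5% | 51.2% | 86.3% |
| 60% | 32 | 5.0% | 5.3% | 6.9% | 13.2% | 24.6% |
| 75% | 180 | 5.0% | 7.3% | 20.6% | 66.1% | 96.6% |
| 75% | 32 | 5.0% | 5.4% | 7.6% | 16.8% | 34.9% |

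The 60% is the SAP's SC figure for satisfaction with time to result, borrowed because the documents give no rate for willingness to recommend. The 75% and every value of d are assumptions.

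**The case against.** The strongest reply is that much of the mechanism has to be supplied by the reader, and most of that reply stands.

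- **Same person, same contact, interview.** A reader might infer that one RA explains the result and then questions the same patient face to face. The text names a role, and several RAs are to be assigned. The mode of collection is not stated, and a self-completed form is compatible with the wording.
- **Who delivers the script.** Two other places in the protocol point to clinicians. If they deliver it, the RA's courtesy effect largely disappears. This is why reconciliation comes first.
- **An effect in EXP only.** The Day 0 line is not limited to EXP, and antigen results in standard care are back in 15 to 20 minutes. An RA might communicate same-day results in both arms. Some courtesy would then be shared, and only the difference between arms would bias the comparison. For this reason d is defined as a net shift.
- **Intervention or artefact.** Satisfaction with a good explanation belongs to the randomised EXP strategy. Only the part due to rating the visit in front of the communicator is bias, so a positive primary could not simply be put down to the interviewer.

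What the reply does not remove is that the protocol gives both tasks to one role, for an open and subjective primary, and describes no safeguard.

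**Conclusion.** The point holds as a risk of differential interviewer bias in the primary, most plausibly towards EXP. A reader might go further and conclude that the primary is biased. The documents do not support that: they contain no measured effect and do not settle who speaks to the patient or how the rating is taken.

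The size is illustrative only. With 60% favourable in SC, a net shift of 5 or 10 points would raise the false-positive rate from 5% to about 17% or 51% at 180 per arm, but only to about 7% or 13% at 32 per arm. These figures rest on no true effect, a dichotomised primary, 1:1 allocation and the assumed shift.

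Confidence is moderate. This is a cheap improvement to the method of collection.

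**What to change.** 1. Reconcile Outcome Measures with Processing Samples and the barriers section: state who communicates results and the script, to whom, and in which arm.
2. Reword the Day 0 line so that, in both arms and at the same point of the visit, the patient completes the rating privately on paper or tablet, unseen by whoever communicated the result. The age criterion mentions 7 years, so children may be enrolled: provide for a parent or guardian to complete it for or with the child. Provide neutral help for patients with low literacy.
3. Have providers complete their survey in the same private way.
4. Where rosters allow, give each Day 7 call to an RA who did not see that patient on Day 0. With several RAs already assigned, this should need no new staff.

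The cost is a wording change, a self-complete form and some rostering. Expect a few more skipped items. Patients will still know their arm, so some open-label bias remains and the report should say so.

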Statistical Analysis Plan

Study Name:

Urgent Care Management of Respiratory Illness Enabled with Novel Testing Pathway (URGENT): A Randomized Control Trial of Respiratory PCR versus Standard Care

Date: 13-Feb-2024

NCR: NCR213901

Principal Investigator:

Name: **[name] MD, MS**
Title: **Associate Professor of Emergency Medicine**
Institution: **George Washington University**

Statistical analysis: Categorical variables are expressed as absolute frequencies and percentages. Continuous variables are presented as the mean and standard deviation (SD) or as the median and interquartile range (IQR) when not normally distributed. Categorical variables were compared using the chi-squared test or Fisher's exact test. Continuous variables were compared using the Student's *t*-test or Mann–Whitney U test, according to the Kolmogorov–Smirnov test of normality. All results were considered statistically significant at $P < 0.05$. All analyses were performed using R version 4.1.1 (Comprehensive R Archive Network). The sample size was based on the expected high satisfaction for time to result in 90% of patients in the syndromic assessment group versus 60% of those in the SOC group with a power of 0.8 and a significance value of 0.05.

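### Day 7 satisfaction and understanding would be compared only among patients reached by phone, although the same items are recorded at Day 0 and could be used for those who are not reached

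*Protocol*

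**What the plan says.** Under Aim 1 the protocol makes satisfaction with urgent care the primary outcome ("willingness to recommend urgent care versus others). Day 0") and lists the same item as a secondary outcome a week later ("willingness to recommend urgent care versus others). Day 7"). Understanding of the disease process is listed for both days. All seven Aim 1 secondary outcomes have a Day 7 assessment.

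The Day 7 entry under Outcome Measures has two lines: "Review of EHR (Allscripts, CRISP") and "Patient follow-up assessment performed by phone". It does not say which outcome comes from which source. Data Collection adds health literacy and insurance status.

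The SAP is one paragraph. On comparisons it says "Categorical variables were compared using the chi-squared test or Fisher's exact test" and "Continuous variables were compared using the Student's *t*-test or Mann–Whitney U test". Neither document gives a Day 7 analysis set, an expected loss, a missing-data method or a sensitivity analysis for patients who are not reached.

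**The concern.** The SAP does not use the term complete case, but the tests it names can use only observed values. For an item asked by phone, that means patients who answered.

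A patient who left dissatisfied on Day 0 is plausibly harder to reach on Day 7 and more likely to be dissatisfied then. The protocol expects satisfaction to be higher with RP2.1, so the share of such patients is expected to differ between arms. The reach pattern itself could also differ. EXP patients receive a scripted explanation and SC patients standard communication. In the standard-care pathway, "for patients with a negative test, no call is made and patients must access the patient portal to get results".

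At stake is the reading of the Day 7 patient-reported results: a difference among respondents may partly reflect who answered the phone. The Day 0 value of the same item would help to separate the two, and the SAP does not use it.

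**Working it through.** The documents state no Day 7 reach rate and no Day 7 satisfaction rate, so there is no planned figure to reproduce. All inputs below are assumptions, chosen to show a range.

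**Inputs.** Satisfied at Day 0: 80% EXP, 65% SC. Satisfied at Day 7: 90% of those satisfied at Day 0 and 30% of those not, in both arms.

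**True Day 7 rates.** EXP: 0.80 × 0.90 + 0.20 × 0.30 = 0.78. SC: 0.65 × 0.90 + 0.35 × 0.30 = 0.69. The difference is 9.0 points.

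**Rate among respondents.** Let p be the Day 0 satisfied share, and rs and ru the reach rates of patients satisfied and not satisfied at Day 0. The satisfied share among those reached is w = p·rs / (p·rs + (1 − p)·ru). The observed Day 7 rate is 0.90w + 0.30(1 − w).

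| Reach, EXP (rs/ru) | Reach, SC (rs/ru) | w, EXP | w, SC | Observed EXP | Observed SC | Difference |
|---|---|---|---|---|---|---|
| 0.80/0.55 | 0.80/0.55 | 0.640/0.750 = 0.853 | 0.520/0.7125 = 0.730 | 0.812 | 0.738 | 7.4 points |
| 0.85/0.75 | 0.80/0.45 | 0.680/0.830 = 0.819 | 0.520/0.6775 = 0.768 | 0.792 | 0.761 | 3.1 points |
| 0.80/0.45 | 0.85/0.75 | 0.640/0.730 = 0.877 | 0.5525/0.815 = 0.678 | 0.826 | 0.707 | 11.9 points |

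The denominators of w are the overall reach rates, so these rows imply a loss of 17% (1 − 0.830) to about 32% (1 − 0.6775) per arm.

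**A second set of inputs.** With Day 0 satisfaction of 90% vs 60%, the same 90%/30% carry-over, and reach of 90% if satisfied and 60% if not in both arms, the true Day 7 difference is 0.840 − 0.660 = 18.0 points. Respondents show 0.859 − 0.715, or 14.3 points before rounding. The SAP's 90% and 60% refer to satisfaction with time to result and are borrowed here only as an example.

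**When there is no bias.** With the same Day 0 satisfaction in both arms (60% vs 60%), the same carry-over and the same reach pattern, w is identical in the two arms. The observed difference is then 0, which is the truth.

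**When the null test is affected.** Suppose there is no true effect (60% vs 60%, 180 per arm, assuming the projected 360 are split 1:1). Suppose too that reach depends on Day 7 satisfaction in SC only: 90% if satisfied and 80%, 70%, 60% or 50% if not, against 90% for everyone in EXP. The chance of P < 0.05 is then about 8%, 19%, 39% or 65%.

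**What the Day 0 value adds.** In the 9.0-point scenarios, respondents within each Day 0 group show the true 90% and 30%. Applying these to the Day 0 split of all randomised patients gives 0.78 and 0.69 again, hence 9.0 points in all three rows. This follows from letting reach depend only on arm and Day 0 satisfaction. It shows what the method can do if that holds, not that it holds.

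**The case against.** The strongest reply is that nothing in the documents shows informative loss. Reach may be high: the protocol budgets 21 assistant-hours a week for follow-up and survey against 30 enrolments, and 21 × 60 / 30 = 42 minutes per patient. The 3.1 and 11.9 points need reach patterns that differ by arm, and they lie on opposite sides of the truth. With a common pattern the shift is only from 9.0 to 7.4 points; as an odds ratio, from about 1.59 to 1.53. All of this stands, and it is why no size or sign is claimed.

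A reader might also infer more than the documents support:

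- That contact by a research assistant on Day 0 is confined to EXP. Outcome Measures lists communication of results on Day 0 without naming an arm. Under Standard care, patients with a positive result are telephoned, and non-RP2.1 tests are allowed in both groups. What differs by arm is scripted versus standard communication. A link from that to answering the Day 7 call is conjecture.
- That the EHR goes unused for additional tests. The Day 7 entry does not limit the EHR review to patients reached, and the EHR may already be the intended source. The gap is that the source is not specified.
- That an EHR count is free of problems. Under Standard care, a negative antigen test leads to a send-out confirmatory PCR. Without a rule that excludes it, the count could be raised in SC by routine testing alone.
- That imputation removes the bias. It does not if reach depends on experience after Day 0, such as the wait for a send-out PCR result, typically 24 to 96 hours.

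**Conclusion.** The point holds as a conditional one about secondary outcomes. The named tests would analyse Day 7 satisfaction and understanding in respondents only. If reach depends on satisfaction, the risk difference can be biased when satisfaction differs between arms or when the reach pattern does.

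It would be too strong to say that the Day 7 contrasts are biased, or in which direction. Under the stated assumptions a true 9.0 points could appear as anything from 3.1 to 11.9, and with other reach rates the range would change. Nor does the point reach the primary outcome, which is taken on Day 0 and does not depend on the call.

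The change is worth making because it is cheap and uses data the trial already plans to collect.

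**What to change.** In the SAP:

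- Analyse Day 7 satisfaction and understanding in all randomised patients by multiple imputation done separately by arm, with the Day 0 value of the same item, health literacy, insurance status and site in the model.
- Keep the respondents-only test as a sensitivity analysis. Add a delta-adjusted analysis in which imputed values for unreached patients are made progressively worse, with the shift allowed to differ by arm, because imputation alone does not cover loss driven by Day 7 experience.
- Report Day 7 reach by arm and by Day 0 satisfaction. The counts by arm also serve the reader of the other phone-based outcomes (isolation, missed work, tests of contacts), for which no specific method is proposed here.
- For additional diagnostic tests of the patient, count EHR-recorded tests for every randomised patient in both arms by one rule that excludes index-visit testing, including the routine confirmatory send-out PCR. Report phone-reported tests separately.

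The cost is SAP wording and a little more analysis, with no new data collection. Two limits remain: imputation corrects only loss explained by recorded data, and EHR counts miss tests done at home or outside the linked records. The SAP is dated 13 February 2024, after the enrolment period anticipated in the protocol. If outcome data have already been seen, the added analyses should be labelled with their timing.
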